### 6.4.2 Best Response

The determination of antitumor activity will be based on objective response assessments made by the investigator according to the RECIST v1.1 (Eisenhauer 2009). Only response assessments on or prior to the start date of any new anticancer therapy will be considered for best response. The patient’s best confirmed response will be the best demonstrated response to date that has been confirmed, when confirmation is required (i.e. for PR and CR only). When confirmation is not required, the patient’s best response will be the best demonstrated response to date. The patient’s best response will be used in determining the ORR.

A response (CR or PR) will be considered confirmed if the subsequent disease assessment conducted no earlier than 4 weeks after the initial response still shows CR or PR (i.e., CR followed by CR or PR followed by PR or CR). A patient will have a best response of SD if there is at least one SD assessment (or better)  $\geq 5$  weeks after the start of treatment and the patient does not qualify for confirmed CR or PR. RECIST v1.1 outlines scenarios for best overall responses when confirmation of CR and PR is required.

In addition to radiographic tumor assessments, expression level of CA-125 will also be monitored to assess CA-125 response according to the GCIG criteria.

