9.3 Statistical and Analytical Plans

The statistical and analytical plans presented below summarize the more complete plans to be detailed in the statistical analysis plan (SAP). A change to the data analysis methods described in the protocol will require a protocol amendment only if it alters site conduct (e.g., adding baseline assessments to define a subgroup). The SAP will be finalized prior to database lock. Any changes to the methods described in the final SAP will be described and justified in the clinical study report.

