APPENDIX G: RECIST CRITERIA SUMMARY (VERSION 1.1)

Response Evaluation Criteria in Solid Tumors	
Term	Definition
Complete response (CR)	Disappearance of all target lesions. Any pathological lymph nodes must have reduction in short axis to <10 mm.
Partial response (PR)	At least a 30% decrease in the sum of diameters of target lesions, taking as reference the baseline sum diameters.
Progressive disease (PD)	At least a 20% increase in the sum of diameters of target lesions, taking as reference the smallest sum on study (this includes the baseline sum if that is the smallest on study). In addition to the relative increase of 20%, the sum must also demonstrate an absolute increase of at least 0.5 cm. The appearance of one or more new lesions is also considered progression.
Stable disease (SD)	Neither sufficient shrinkage to qualify for PR nor sufficient increase to qualify for PD, taking as reference the smallest sum diameters while on study.
Measurable lesion	Must be accurately measured in at least one dimension (longest diameter in the plane of measurement is to be recorded) with a minimum size of 10 mm by CT scan (CT slice thickness no greater than 5 mm).

From RECIST Version 1.1 ([Eisenhauer 2009](#))

A response (CR or PR) will be considered confirmed if the following disease assessment (at least 4 weeks after the initial response) still shows response (CR or PR). In cases where the initial response is followed by SD, it will be considered as confirmed if the SD is later followed by PR or CR. For example, if a patient had PR in week 6, SD in Week 12, and PR in Week 18, this PR will be considered as confirmed.

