## 6.2 Determination of Sample Size

Up to approximately 222 patients may be enrolled in the study. This includes approximately 6–12 patients in the safety run-in phase, approximately 30 patients in each of 2 randomized Part A cohorts, and the possible expansion of an additional 70 patients in one of the 2 Part A cohorts. Part B will enroll approximately 80 patients including approximately 60 patients who have received 1 to 3 prior lines of therapy, including bevacizumab treatment.

Analysis regarding expansion of Part A will be conducted when approximately 30 patients per cohort have at least one post-baseline response assessment per RECIST v1.1 or have discontinued from the study or started subsequent cancer therapy.

A cohort may be expanded to further characterize antitumor activity if the safety profile is acceptable, other efficacy endpoints are comparable to current standard of care, and the number of confirmed CR or PR meet cohort-specific criteria.

The sample size is not based on power calculations for formal hypothesis testing, but is selected based on ORR estimate precision as characterized by 95% confidence intervals (CIs). For a sample size of 30 patients (Part A) and 60 patients (Part B with 1 to 3 prior lines of therapy, including bevacizumab treatment) per cohort (or 100 patients, if a treatment arm from Part A is expanded), assuming the confirmed ORR is between 20% and 40%, the 2 -sided 95% exact CIs are summarized below.

Confirmed ORR	95% Exact CI (N=30)	95% Exact CI (N=60)	95% Exact CI (N=100)
15%	(4%, 31%)	(7%, 27%)	(9%, 24%)
20%	(8%, 39%)	(11%, 32%)	(13%, 29%)
30%	(15%, 49%)	(19%, 43%)	(21%, 40%)
40%	(23%, 59%)	(28%, 53%)	(30%, 50%)

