### 7.5.1 Primary Endpoint

#### 7.5.1.1 Confirmed Objective Response Rate (ORR)

The primary efficacy endpoint of this study is the confirmed ORR per investigator assessment. The confirmed ORR is defined as the proportion of patients who achieve a confirmed CR or PR according to RECIST v1.1 (Eisenhauer 2009). Patients who do not have at least 2 post-baseline response assessments (initial response and confirmation scan) will be counted as non-responders. Confirmation means a PR is followed by a PR or CR at least 4 weeks later, or a CR is followed by a second CR at least 4 weeks later.

The confirmed ORR of each cohort and its exact 2-sided 95% CI will be calculated.

This endpoint will also be summarized by the subgroups defined in Section 6.8.

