### 7.5.2 Secondary Endpoints

#### 7.5.2.1 Confirmed and Unconfirmed ORR

Confirmed and unconfirmed ORR is defined as the proportion of patients who achieve a CR or PR according to RECIST v1.1 as assessed by the investigator. These include patients with confirmed responses as well as those whose responses were not confirmed or had not yet been assessed for confirmation. Patients who do not have at least 1 post-baseline response assessment will be counted as non-responders.

The confirmed and unconfirmed ORR will be estimated for each cohort and its exact 2-sided 95% CIs will be calculated.

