#### **7.5.2.5 Duration of Response**

DOOR is defined as the time from the first documentation of objective response (CR or PR that is subsequently confirmed) to the first documentation of PD or death due to any cause, whichever comes first.

DOOR data will be censored as described below:

- Patients who do not have PD and are still on study at the time of an analysis will be censored at the date of last disease assessment documenting absence of PD.
- Patients who have started a new anticancer treatment prior to documentation of PD will be censored at the date of last disease assessment prior to the start of new treatment.
- Patients who are removed from the study prior to documentation of PD will be censored at the date of last disease assessment documenting absence of PD.
- Patients who have death or PD after two or more consecutive missed/NE tumor assessments will be censored at the date of the last adequate tumor assessment prior to the missed visits.

DOOR will only be calculated for patients who achieve a confirmed CR or PR according to RECIST v1.1 as assessed by the investigator.

DOOR will be analyzed by cohort using the Kaplan-Meier methodology and Kaplan-Meier plots will be provided. The median DOOR and its 2-sided 95% CI will be calculated as appropriate.

Sensitivity analyses may be performed for DOOR to evaluate the robustness of treatment effects:

- A sensitivity analysis may be performed by considering death or PD per RECIST v1.1 as an event regardless of missing disease assessments.
- A second sensitivity analysis may be performed for DOOR to evaluate the robustness of results by including investigator claim of clinical progression as an event. Patients who are not evaluable or have a response of SD or better per RECIST v1.1 at the same visit as investigator claim of clinical progression will be counted as disease progression (i.e., an event). The date of progression will be the date of investigator claim of clinical progression or PD date per RECIST v1.1, whichever is earlier.

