## 8 INTERIM ANALYSIS

A safety analysis will be conducted 28 days after all patients at the 0.9 mg/kg dose level in the safety run-in portion have received at least one dose of study treatment to evaluate the tolerability of the dose-dense regimen. If applicable, a second safety analysis will be conducted 28 days after all patients at the 1.2 mg/kg dose level have received at least one dose of study treatment. A safety monitoring committee (SMC), consisting of the investigators, study medical monitor, biostatistician, and drug safety representative, will review the safety data before proceeding to Parts A and B.

Interim analysis for futility will be performed on Part B after at least 20 patients with 1 to 3 prior lines of therapy, including bevacizumab treatment, have been treated and had at least one response assessment post-baseline.

The Bayesian predictive probability approach will be used to assess the futility criteria (Lee 2008). At the time of the interim futility analysis, the PPoS will be calculated. PPoS is the probability of achieving “success” should the cohort be continued to the maximum sample size of 60 in the target population (1 to 3 prior lines of therapy, including bevacizumab treatment) given the data observed at interim, and the cohort is considered “success” if the posterior probability that the ORR exceeds the response rate of current standard of care (i.e., 12% as reference in Section 3.2) is greater than 70%.

Both the confirmed and unconfirmed CR or PR observed at interim will be counted as a response for the calculation of PPoS. It is appropriate to include the unconfirmed response for the purpose of interim analysis because based on the estimates from GEN701 trial, about 60% of the responders will respond at their first post-baseline scan and approximately 75% of the confirmed/unconfirmed responses will eventually be confirmed. Table 1 summarizes the PPoS based on the number of responses observed among the first 20 patients.

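### The confirmation rule for the primary endpoint differs between Protocol Appendix G and SAP 6.4.2, and SAP 7.5.1.1 does not settle it: PR–SD–PR is a confirmed response under the first and not under the second.

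*SAP*

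**What the plan says.** Protocol 9.2.1 defines the endpoint as the proportion with a confirmed CR or PR but does not spell out which scan sequences count. Three other places do.

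- **Protocol Appendix G** starts with a base rule: the next assessment, at least 4 weeks on, must still show CR or PR. It then adds an exception for a response followed by SD: "it will be considered as confirmed if the SD is later followed by PR or CR". Its example is PR at Week 6, SD at Week 12 and PR at Week 18, which counts as confirmed.
- **SAP 6.4.2** keeps only the base rule: a response is confirmed if "the subsequent disease assessment conducted no earlier than 4 weeks after the initial response still shows CR or PR". It closes with a general pointer to RECIST v1.1 scenarios and says nothing about an intervening SD. The same section says that best response feeds the ORR.
- **SAP 7.5.1.1**, the primary-endpoint section, says "Confirmation means a PR is followed by a PR or CR at least 4 weeks later". It does not say that the later scan must be the next one, and it does not mention SD.

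SAP 9.1 lists no change from the original protocol. SAP 9.2 says the SAP was updated to align with Amendment 4.

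**The concern.** Appendix G needed a separate sentence to admit PR–SD–PR, so its base sentence does not cover that sequence. SAP 6.4.2 reproduces the base sentence without the exception. The protocol's own example is then a responder in one document and a non-responder in the other.

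Four results depend on which passage is programmed: confirmed ORR and its interval, the patients entering DOR, the TTR responders, and the Part A expansion criterion that "the number of confirmed CR or PR meet cohort-specific criteria". Response start dates can also move when ORR does not. The study is open-label with investigator-assessed response, so choosing the rule once the sequences are visible would make the primary result look data-dependent.

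A smaller mismatch is CR followed by PR. Appendix G's general wording would confirm it; neither SAP section lists it. It should be rare, because regrowth of 0.5 cm or more after a non-nodal CR would usually be PD under Appendix G.

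**Working it through.** **1. The plan's own precision figures.** The exact (Clopper–Pearson) limits are the 2.5% quantile of Beta(x, n−x+1) and the 97.5% quantile of Beta(x+1, n−x). For 20% they give:

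- 6/30: 7.7–38.6%
- 12/60: 10.8–32.3%
- 20/100: 12.7–29.2%

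These match the SAP 6.2 table. All 12 cells reproduce, taking the 15% row at N=30 as 4/30 (13.3%; 3.8–30.7%). The planned figures are sound; the problem is the definition.

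**2. The three wordings applied to example sequences.** SAP 7.5.1.1 is read here as accepting any later scan at least 4 weeks on.

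| Sequence | Appendix G | SAP 6.4.2 | SAP 7.5.1.1 |
|---|---|---|---|
| PR wk 6, PR wk 12 | confirmed | confirmed | confirmed |
| PR wk 6, SD wk 12, PR wk 18 | confirmed | not confirmed | confirmed |
| PR wk 6, SD wk 12, PR wk 18, PR wk 24 | confirmed | confirmed | confirmed |
| CR wk 6, PR wk 12 | confirmed | not confirmed | not confirmed |

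If 7.5.1.1 is instead read as meaning the next scan, its second row becomes not confirmed.

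**3. Effect of one reclassified patient on confirmed ORR.** The shift is 1/N: 1/30 = 3.3 points, 1/60 = 1.7 points, 1/100 = 1.0 point.

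- N=30: 5/30 = 16.7% (5.6–34.7) becomes 6/30 = 20.0% (7.7–38.6).
- N=60: 8/60 = 13.3% (5.9–24.6) becomes 9/60 = 15.0% (7.1–26.6).

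**4. Effect on dates when ORR does not change.** In PR–SD–PR–PR (row 3), the first confirmed response is at Week 6 under Appendix G. Under SAP 6.4.2 it is at Week 18, the first PR whose next scan is also PR. The difference is 18 − 6 = 12 weeks = 84 days, added to TTR and taken from DOR. SAP 7.5.1.1 gives Week 6 only on the any-later-scan reading.

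**5. Ceiling on the ORR effect.** The documents give no frequency for PR–SD–PR, so only an upper bound is possible, and it assumes the earlier trials used the strict rule. SAP 8 expects that "approximately 75% of the confirmed/unconfirmed responses will eventually be confirmed", which leaves about 25% unconfirmed. The earlier ovarian data in Protocol 1.3.3.2 show 3 of 6 and 2 of 4 responses confirmed, so 5 of 10 unconfirmed. Assume 12 responses among 60 patients (20%):

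- 12 × 0.25 = 3 patients, 3/60 = 5.0 points
- 12 × 0.50 = 6 patients, 6/60 = 10.0 points

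The true number is lower, because many unconfirmed responses end in PD or have no later scan.

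**6. A benchmark, not a decision rule.** Protocol Appendix I uses a Beta(0.12, 0.88) prior, and success means a posterior probability above 70% that ORR exceeds 12%. The calculation reproduces the plan's PPoS table (for example 19.6%, 48.6% and 77.2% for 2, 3 and 4 responses, against 20%, 49% and 77%). Assuming the criterion were applied to confirmed ORR at N=60, the posterior is Beta(0.12+x, 0.88+60−x). This gives 58.6% at x=8 and 72.5% at x=9, so one patient at that margin would cross the line.

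**7. What is not affected.** The interim futility count includes unconfirmed responses. The Week 6/12/18 patient has disease control under either rule, through her SD at Week 12. For the confirmed-and-unconfirmed ORR, SAP 7.5.2.1 says "These include patients with confirmed responses as well as those whose responses were not confirmed". It therefore counts every disputed patient and bounds the ORR effect from above, but it does not settle the DOR and TTR dates.

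**The case against.** The strongest reply is that SAP 6.4.2 never names PR–SD–PR and may be an incomplete copy of Appendix G rather than a contrary rule. It points to RECIST v1.1, and 7.5.1.1 can be read consistently with Appendix G. This does not rescue the text. The pointer states no rule for an intervening SD, and reading one into it would set 6.4.2 against its own preceding sentence. An incomplete copy still gives the programmer the wrong classification.

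The objections about size largely stand:

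- **Rarity.** By target-lesion sums, a PR is at most 70% of baseline. Rising above that without PD means an increase of less than 20% from nadir, so a nadir above 0.70/1.20 = 58.3% of baseline, or an increase of less than 0.5 cm. For baseline sums of about 43 mm or more, only PRs of roughly 30–42% shrinkage can pass to SD, and the tumour must then shrink again.
- **Dates.** Protocol 7.2 illustrates an extra confirmatory scan at Week 10. With PR Week 6, SD Week 10, PR Week 12 and PR Week 18, the start moves 6 weeks (42 days), not 12.
- **Ceiling inputs.** The earlier ovarian data pool two regimens, neither of them Part B's, and GEN701 expansion was ongoing at its cutoff.
- **Expansion.** That analysis can run after one post-baseline scan, and PR–SD–PR needs three.
- **SAP 9.1.** Its heading refers to the original protocol, so the alignment statement in 9.2 is the better evidence.

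The SAP may also adopt a stricter rule without an amendment. But it declares no such choice, and its two sections do not give one rule.

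**Conclusion.** The concern holds. Followed as written, SAP 6.4.2 classifies the protocol's own worked example the opposite way, and SAP 7.5.1.1 does not resolve it. This should be fixed before database lock. It does not threaten the design: the analysis is descriptive, with no formal hypothesis test, and the affected patients are probably few.

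The firm figures are the per-patient ORR shifts. A start-date shift of 6 to 12 weeks follows for the example schedules. The 5 to 10 points is a ceiling under stated assumptions, not an estimate, and the 58.6% and 72.5% posteriors rest on applying an interim success criterion to final confirmed ORR, which the plan does not say it will do.

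**What to change.** Before database lock, put one confirmation algorithm in SAP 6.4.2. It should state:

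- how an intervening SD is handled;
- how CR followed by PR is handled;
- which scan date starts the response in PR–SD–PR.

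Have SAP 7.5.1.1, DOR, TTR, DCR and the Part A expansion count refer to it. Use Appendix G for the primary analysis so that the SAP matches the protocol, and report the strict next-assessment rule as a sensitivity analysis of confirmed ORR. If the strict rule is preferred as primary, declare it in SAP 9.1 as a change from the protocol.

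The cost is SAP wording and one extra table row. Scanning and data collection do not change. Protocol 9.3 says "A change to the data analysis methods described in the protocol will require a protocol amendment only if it alters site conduct", and this does not.

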#### **6.4.3 Response Assessment Dates**

For efficacy assessments, the date of response assessment of CR, PR, or SD will be the latest of all radiologic scan dates for the given response assessment. The date of progression per RECIST v1.1 will be the earliest of all radiologic scan dates that PD response has been documented, i.e., the earliest of

- Date(s) of target lesion assessments with target lesion response of PD
- Date(s) of non-target lesion assessments with lesion status of unequivocal progression
- Date(s) of documenting new unequivocal lesion(s)

#### **6.5 Handling of Dropouts and Missing Data**

Missing data will not be imputed unless otherwise specified. Missing AE start date and/or end date will be imputed while calculating duration of events and treatment-emergent status (see Appendix A for imputation details).

For time-to-event endpoints, e.g., DOR, PFS, and OS, patients who have no specific event will be censored as specified for each respective endpoint in Section 7.5.

Patients who do not have at least 2 post-baseline response assessments (initial response and confirmation scan) will be counted as non-responders for analysis of the primary endpoint.

Missing subsequent anticancer treatment start date will be imputed while deriving the time-to-event endpoints as applicable (see Appendix B for imputation details).

For prior therapies end dates, if month and year are present and only day is missing, day may be imputed. The end day will be imputed with the last day of the month or 21 days before the first dose of study drug, whichever is earlier. If the imputed end date is earlier than start dates, the end day will be imputed with the day after the start date. If month or year is missing, no imputation will be performed.

For prior therapies start dates, if month and year are present and only day is missing, day may be imputed. The imputed day will be the first day of the month. If month or year is missing, no imputation will be performed.

Unless otherwise specified, if the numeric value of a clinical laboratory test is not available because it is below the lower limit of quantification (LLOQ), “< LLOQ” should be used whenever applicable. In cases where a numeric value is required, e.g., calculating the mean and standard deviation, the LLOQ/2 will be used for the calculation.

#### **6.6 Multicenter Studies**

There are multiple centers in this study, however it is not anticipated that any center will accrue enough patients to warrant an analysis by center.

## **6.7 Multiple Comparison/Multiplicity**

No multiple comparisons are planned in this study.

## **6.8 Examination of Subgroups**

Subgroups would be conducted for the primary endpoint (confirmed objective response rate) and other key secondary efficacy endpoints if appropriate. Subgroups may include but are not limited to the following:

- Age (18–64,  $\geq 65$  years old)
- Platinum-free interval (<3 vs 3-6 month)
- First line vs. second line PROC
- TF expression (less than or equal to median, above median)
- Prior treatment with CPIs (yes, no)
- Prior treatment with PARP inhibitors (yes, no)
- ECOG performance score at baseline (0, 1)
- Number of prior systemic therapies (including in the PROC setting) (1, 2, 3,  $\geq 4$ )

Platinum-free interval is defined as the time from the end of the latest platinum-based therapy to the earlier of disease progression from the latest platinum-based therapy or the start of the first line systemic therapy in the PROC setting.

If the number of patients in some subgroups is not sufficiently large (e.g., <10% of the total sample size), the subgroup analysis may not be performed or the subgroups may be combined if applicable.

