4.1 Inclusion Criteria

1. Histologic documentation of epithelial ovarian cancer, primary peritoneal cancer, or fallopian tube cancer (excluding carcinosarcoma, mucinous, and low grade serous histologies), hereafter referred to as “ovarian cancer”.
2. Safety run-in patients only: Platinum-resistant ovarian cancer (PROC), which is defined as having progressed or relapsed within 6 months after previous platinum-containing chemotherapy and for which single agent chemotherapy is appropriate. Progression or

relapse must be documented radiographically using RECIST v1.1 criteria. The patient may have received more than 1 prior systemic treatment regimen in the PROC setting.

3. Part A and Part B patients only: PROC; with the following prior treatment requirements:

- The patient must have received 1 to 3 prior anticancer lines of therapy overall, including at least 1 line of therapy containing bevacizumab or a biosimilar to bevacizumab.
- Adjuvant ± neoadjuvant are considered 1 line of therapy.
- Patients may have received a PARP inhibitor or an immuno-oncology (IO) agent; any of these regimens are to be considered a line of therapy for the purposes of this study if not used as maintenance therapy.
- Maintenance therapy (including bevacizumab, PARP inhibitors and IOs) will be considered part of the preceding line of therapy and not to be counted as a new line of therapy.
- Any chemotherapy regimen change due to toxicity in the absence of disease progression is considered as part of the same line of therapy.
- Hormonal therapy will not be counted towards the lines of therapy.

4. Measurable disease according to RECIST v1.1 as assessed by the investigator, defined as:

- a. A minimum of one non-nodal lesion ≥ 10 mm in the longest diameter from a non-irradiated area. If target lesion(s) are located within previously irradiated area only, the patient can be enrolled only if there has been demonstrated progression in the “in field” lesion and upon approval of the sponsor’s medical monitor.

OR

- b. Lymph node lesion ≥ 15 mm in the shortest diameter from a non-irradiated area.

5. Age 18 years or older.

6. An Eastern Cooperative Oncology Group (ECOG) Performance Status score of 0 or 1 (see [Appendix E](#) for conversion of performance status using Karnofsky and Lansky scales, if applicable).

7. The following baseline laboratory data:

- Absolute neutrophil count (ANC) $\geq 1500/\mu\text{L}$ assessed at least 2 weeks after growth factor support, if applicable.

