## **7.2 Demographic and Baseline Characteristics**

Demographics and baseline characteristics, including age at consent, gender, ethnicity, race, baseline height, weight, and ECOG score will be listed and summarized by cohort and total using the FAS. Disease specific characteristics will be listed and summarized by cohort and total using the FAS. Disease characteristics may include cancer stage at diagnosis, previous cancer-related treatments, number of prior systemic therapies, number of prior cytotoxic chemotherapy in the PROC setting, platinum-free interval, histology, genetic markers, and tissue factor expression.

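### SAP 6.8 mixes the latest platinum with the first PROC therapy, so some patients with a true 3–6 month platinum-free interval are put in the under-3-month subgroup

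*SAP*

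**What the plan says.** SAP 6.8 gives the derivation in one sentence. The start is set by "Platinum-free interval is defined as the time from the end of the latest platinum-based therapy", and the end is "the earlier of disease progression from the latest platinum-based therapy or the start of the first line systemic therapy in the PROC setting". The subgroup is cut as "Platinum-free interval (<3 vs 3-6 month", with no lower bound at zero and no cell above 6 months.

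The variable is used in two places.

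- **Primary endpoint by subgroup.** SAP 6.8 says "Subgroups would be conducted for the primary endpoint (confirmed objective response rate". SAP 7.5.1.1, on confirmed objective response rate (ORR), adds "This endpoint will also be summarized by the subgroups defined in Section 6.8".
- **Baseline table.** SAP 7.2 lists, among characteristics that may be shown, "number of prior cytotoxic chemotherapy in the PROC setting, platinum-free interval, histology".

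On eligibility for Parts A and B, Protocol 4.1 criterion 3 says "The patient must have received 1 to 3 prior anticancer lines of therapy overall", at least one of them containing bevacizumab or a biosimilar. It does not exclude platinum given after resistance has developed. The only platinum-specific exclusion (Protocol 4.2, criterion 1) concerns progression within 3 months of completing first-line platinum.

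SAP 6.4.1 computes time variables as end date minus start date plus 1 day and converts days to months by dividing by 30.4375. It has no rule for an end date that precedes the start date.

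**The concern.** The two ends of the interval refer to different points in the treatment history. For a patient whose only PROC-setting therapy follows her last platinum, they fall in the right order. For a patient given platinum again after she became resistant, the first PROC-setting therapy is either that same platinum or a regimen before it. The rule then selects a date on or before the day the interval begins.

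A negative platinum-free interval has no meaning, yet the cut at 3 months accepts it silently as a short one. Protocol 1.1 calls this interval a strong predictor of treatment success, so the subgroup is one that readers will look at.

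The under-3-month cell may also be small. Protocol 4.2 criterion 1 removes patients who progressed within 3 months of first-line platinum, so genuine members should mostly have had more than one platinum course. A few misplaced patients could therefore weigh noticeably in that cell.

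**Working it through.** The documents report no figure for this interval, so there is none to reproduce. The check applies the SAP rule literally.

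**Notation.** E = end of latest platinum; P = progression after that platinum; S = start of the first systemic therapy in the PROC setting. From SAP 6.8 and 6.4.1:

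interval = min(P − E + 1, S − E + 1) days; months = days / 30.4375.

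**General result.** If the latest platinum was given in the PROC setting, it is either the first PROC line or a later one. Either way S is no later than the start of that platinum, and so no later than E. Hence S − E + 1 ≤ 1 day, and the interval is at most 1 / 30.4375 = 0.03 months. The 3–6 month cell cannot be reached.

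**Control, no platinum after PROC therapy began.** Platinum ends on day 0, progression is at 4 months and the first PROC line starts at 4.5 months. The interval is 4.03 months (4 months plus the 1-day convention), in the 3–6 cell. The rule works here.

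**Patients given platinum again in the PROC setting.** Platinum durations and true intervals are assumptions, varied over a range. The true intervals tried were 1.03, 3.53, 4.03 and 5.93 months. The SAP value does not depend on them.

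| Latest platinum | Duration of that platinum | SAP interval (months) | SAP cell |
|---|---|---|---|
| Is the first PROC line | single day | +0.03 | <3 |
| Is the first PROC line | 1 month | −0.97 | <3 |
| Is the first PROC line | 2 months | −1.97 | <3 |
| Is the first PROC line | 4 months | −3.97 | <3 |
| Is the first PROC line | 6 months | −5.97 | <3 |
| Starts 4 months after a non-platinum first PROC line began | single day to 6 months | −3.97 to −9.97 | <3 |

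The true intervals of 3.53, 4.03 and 5.93 months belong in 3–6 and are moved to <3. The true interval of 1.03 months stays in <3 with a wrong value.

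**Dated illustration (assumed dates).** First-line platinum with progression at 4 months. Second line, non-platinum with bevacizumab, starts 10 Apr 2020 (S). Third line, platinum, ends 30 Nov 2020 (E). Progression is on 30 Mar 2021 (P). This is three prior lines including bevacizumab.

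- P − E + 1 = 121 days; 121 / 30.4375 = 3.98 months, which belongs in 3–6.
- S − E + 1 = −233 days; −233 / 30.4375 = −7.7 months.
- The SAP takes the earlier date, so the recorded interval is −233 days, in the <3 cell.

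**With the second end point moved** to the first new systemic line after E, the re-treated patients with assumed progression at 3.5, 4 and 5.9 months get 3.5, 4.0 and 5.9 months and fall in 3–6. The one progressing at 1 month stays in <3. The control stays at 4.0 months.

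**The case against.** The strongest reply is that the PROC setting may mean the period after the platinum course whose failure made the patient eligible. On that reading the first PROC-setting therapy always follows the latest platinum, and the second end point is only a fallback for undocumented progression. The problem would then vanish. But neither document says this. The Protocol definitions of PROC refer to completion of platinum-containing therapy, or to previous platinum, without tying either to the most recent course. A programmer following the SAP text has no basis for adding that condition.

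The second reply is that affected patients may be few. The randomisation strata provide only for first- and second-line PROC, and the patient in the dated illustration would be third-line. This is fair about that illustration. It does not cover a patient whose single prior PROC regimen contained platinum: she fits the second-line stratum and is affected. A reader might put a share on the 60 target Part B patients; 5% to 30%, for example, would be 3 to 18 patients. Nothing in the documents supports any such share, and it would count every non-positive value rather than the smaller number who change cell.

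The third reply is that little depends on the result. This largely stands. Protocol 9.3.1.8 calls subgroup analyses exploratory and optional. The SAP 6.8 list is permissive and allows small subgroups to be dropped or combined. SAP 7.5 describes all efficacy analyses as descriptive. Against that, SAP 7.5.1.1 does commit to summarising confirmed ORR by these subgroups.

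A reader might also infer a fault in eligibility, because Protocol 4.1 criterion 2 refers to previous rather than most recent platinum and continues "relapse must be documented radiographically using RECIST v1.1 criteria. The patient may have received more than 1 prior systemic treatment regimen in the PROC setting". That criterion covers only the safety run-in, whose patients are summarised separately and for whom confirmed ORR is not the primary endpoint. It does not show a problem in the Parts A and B subgroup.

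**Conclusion.** The point holds as a minor defect in a derivation rule. On the literal text, a patient whose latest platinum was given in the PROC setting cannot have an interval above +1 day, so she is always placed under 3 months. The cell is wrong only if her true interval is 3 months or more; otherwise only the value is wrong. Patients with no platinum after PROC therapy began are classified correctly.

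The descriptive ORR summary by platinum-free interval and any baseline summary of the interval are exposed. It would be tempting to say that the primary result is compromised, or that the subgroup contrast is wrong as it stands. The documents support neither. The overall confirmed ORR, its exact confidence interval and the predictive-probability futility rule do not use the interval, and the contrast is distorted only to the extent that such patients are enrolled. That number cannot be derived from the documents.

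The conclusion rests on two readings: that the PROC setting can begin before the latest platinum, which neither document rules out, and that the SAP 6.4.1 date rule applies without a floor.

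**What to change.** In SAP 6.8, replace the second end point with the start of the first systemic therapy after the end of that latest platinum-based therapy. State that lines are counted as in Protocol 4.1 criterion 3, where maintenance belongs to the preceding line. Without that clause, maintenance begun soon after platinum could be taken as the end of the interval, and patients now classified correctly would change.

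Add a data check that lists any interval of zero or less for review before the table is produced. The 1-day value from a single-day platinum passes that check but is corrected by the new end point. If any interval exceeds 6 months, report it in a separate category above 6 months. No change to Protocol eligibility is warranted for the sake of a descriptive subgroup.

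The cost is one phrase and one check, using prior-therapy dates of the kind the present rule already needs. It is best made as a SAP amendment before database lock. The trial is open label, so a later repair would be made with the responses in view and, under SAP section 1, would have to be documented in the study report.
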